### **7.2.2 Secondary Implementation Outcomes**

Secondary implementation outcomes will be penetration, acceptability, and implementation costs (**Table 2**):

- Penetration, defined as the proportion of newly diagnosed or previously diagnosed and not currently on ART PWID at test sites who are contacted by a counselor and/or systems navigator and who participate in SNaP sessions
- Acceptability, measured with the OADRI 12-item scale, is the perception that SNaP is agreeable or satisfactory by both PWID clients and test site staff.
- Costs, measured directly as non-research costs, see Sections 7.4 and 8.2.2.

## **7.3. Effectiveness Outcomes**

### **7.3.1 Primary Effectiveness Outcome**

The primary effectiveness outcome is ART uptake among eligible PWID (**Table 2**). ART uptake will be defined as the proportion of PWID receiving SNaP with evidence of an ART-related visit in an ART clinic. Acceptable evidence will include a clinic documentation of ART use or an ART prescription.

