### 1.3. Theoretical Basis for the Implementation Trial

We will assess the effectiveness of two different approaches to implementation: 1) a “standard” multifaceted implementation approach (SA) and 2) a “tailored” approach to implementation (TA). Both will be based upon a rigorous approach to designing the implementation strategies called Intervention Mapping, which is a systematic intervention development protocol that incorporates theory, evidence, and stakeholder perspectives to ensure that intervention components address key determinants of change.

Consistent with best practices in implementation science, our study is guided by theoretical frameworks to inform implementation processes (Intervention Mapping), identify implementation barriers and facilitators (Consolidated Framework for Implementation Research; CFIR), and assess implementation outcomes (Proctor et al.’s implementation outcomes framework). Intervention Mapping provides a methodological framework that will yield standard and tailored approaches to implementation. The CFIR is a comprehensive framework that identifies 39 factors that influence implementation outcomes. We will primarily focus on one of the five CFIR domains, the “inner setting,” which will drive our assessment of HIV test site contextual factors that are likely to vary across sites. These factors include the age, maturity, and size of the test site; norms of the test site; organizational readiness to change; implementation leadership; and implementation climate. We posit that tailoring implementation strategies to address test site context will improve test site context and lead to better implementation and effectiveness outcomes. Proctor et al.’s framework also guides our assessment of key implementation outcomes: fidelity, penetration, acceptability, and cost.

As depicted in the conceptual framework (**Figure 3**), the effectiveness of SNaP scale-up will be determined by the implementation processes as operationalized through the SA and TA approaches. The two implementation approaches, SA and TA, must be implemented well (e.g. with fidelity), which in turn, affects SNaP implementation. Successful implementation of SNaP, with high fidelity, penetration and acceptability will lead to better effectiveness outcomes (ART uptake).

[figure not shown]

FIGURE 3. CONCEPTUAL FRAMEWORK

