### 5.4. Procedures to Identify and Characterize High and Low Performing and Sustaining Sites (Aim 3)

We will identify high and low performing sites in both study arms based on SNaP fidelity and

ART uptake targets for PWID clients. We will assess these characteristics qualitatively and quantitatively.

To assess characteristics of high and low performing sites in depth, we will conduct qualitative interviews with:

- HIV-infected PWID, including those that received SNaP and those that declined,
- systems navigators and psychosocial counselors, clinic staff, and clinic directors in both SA and TA arms.
- Health providers and/or adherence counselors at HIV outpatient clinics near these test sites in both SA and TA arms

We will also assess the characteristics of high and low performing sites based on quantitative characteristics derived from the implementation outcomes, test site demographics, and test site context.

To assess characteristics of high and low sustaining sites in depth, we will conduct qualitative interviews with:

- Systems navigators and psychosocial counselors, clinic staff, and clinic directors in both SA and TA arms.

We will also assess the characteristics of high and low sustaining sites based on quantitative characteristics derived from the implementation outcomes, test site demographics, and test site context.

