#### **5.4.1 High and Low Performing and Sustaining Sites Data Collection:**

In-depth interviews - PWID at high and low performing sites: We will conduct six semi-structured in-depth interviews (IDIs) with PWID in each of three sites of the following four site performance types (12 test sites; 72 interviews): 1) SA low performers; 2) SA high performers; 3) TA low performers; and 4) TA high performers. Three PWID will have participated in SNaP and three PWID will have declined SNaP. We will ask participants about barriers and facilitators to uptake of ART and MAT and ART adherence, attitudes and experiences in the HIV test site, with test site staff, and if appropriate, with navigators and counselors.

In-depth interviews - navigators and counselors, clinic staff, and clinic directors: In these same 12 test sites, we will conduct semi-structured IDIs with navigators/counselors (n=12-24), site staff (n=12), site directors (n=12) and HIV providers (n=12) to inform the context and processes that may underlie SNaP success and failures (total n=48-60, depending on the number of navigators and counselors at each site). Topics will include PWID-related stigma; attitudes toward and experience with SNaP, SA, and TA

implementation packages; competing site priorities; perceptions of rewards and leadership support around SNaP; perceptions of effectiveness of SNaP, SA and TA; availability of technical assistance; beliefs around sustainability of SNaP at their test site; collaboration between HIV test sites and HIV outpatient clinics.

Quantitative characterization of high and low performing clinics: We will use the implementation test site context scales for readiness to change, implementation leadership, and implementation climate to characterize each clinic before and after implementation of SNaP. We will also characterize the test sites in terms of overall size (number of HIV tests performed), PWID size (number of HIV tests performed who are PWID), PWID proportion (number of PWID over total tests performed), staff information and current support from NGOs Clinic and PWID characteristics will be assessed before and after implementation.

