#### ***5.5.1 Visit Procedures for PWID Participants: Post-implementation (Appendices I-III)***

If the PWID accepts the SNaP intervention and is eligible and willing to participate in the implementation trial, the following procedures will occur as part of study enrollment:

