###### ***12-Month and 24-Month Follow-up Procedures:***

Administrative, Behavioral, and Regulatory Procedures

- None
  - No direct contact with participant for follow-up procedures
  - Only the participant's ID will be used at ART and/or MMT clinic if the participant presents to either of those clinics after enrollment

Laboratory Evaluations

- None

***Post-24-Month Assessment Qualitative Interview Procedures [among randomly selected PWID at 12 selected sites] (see Section 5.4.1):***

Administrative, Behavioral, and Regulatory Procedures

- Informed consent to participate in qualitative in-depth interview
- Qualitative in-depth interview

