## 8.2. Statistical Analyses and Data Management

### 8.2.1 Implementation and Effectiveness Outcomes Analyses (Aim 1)

We will conduct intent-to-treat comparisons between arms, using a generalized linear regression model with an identity link and Gaussian error distribution to compare means (e.g., fidelity scores) or an identity link and binomial error distribution to compare proportions (e.g., ART uptake). For patient-level outcomes (e.g. ART uptake), the design effect introduced by clinic-level randomization will be addressed using a robust variance estimate.

Data for all aims will be managed at the UNC-Vietnam. Each site will undergo explicit training in data quality. All data sources, including electronic surveys, paper forms, and audio-recordings will be monitored for quality and completeness. Data queries will be made promptly to the sites, typically within one week. The central data team head will have group quarterly calls with site data representatives to address any ongoing data issues. Specific sites will have calls as needed.

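### ART uptake, the primary effectiveness outcome, has two denominators, and the defining one, read literally, counts only PWID who received SNaP

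*Combined protocol and SAP*

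**What the plan says.** Section 7.3.1 opens with "The primary effectiveness outcome is ART uptake among eligible PWID". Its next sentence gives the definition: "ART uptake will be defined as the proportion of PWID receiving SNaP with evidence of an ART-related visit in an ART clinic". Section 8.2.1 says of the analysis: "We will conduct intent-to-treat comparisons between arms".

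Section 5.5.1 introduces the enrollment steps with the condition "If the PWID accepts the SNaP intervention and is eligible and willing to participate in the implementation trial".

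Several sections show that receipt of SNaP is not universal:
- Section 5.2 provides SNaP to those who accept it.
- Section 5.4 plans interviews with "HIV-infected PWID, including those that received SNaP and those that declined".
- Section 5.4.1 gives the split at each selected site: "Three PWID will have participated in SNaP and three PWID will have declined SNaP".
- Section 7.2.2 makes contact with and participation in SNaP a secondary implementation outcome, penetration.

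Other sections describe the ART outcome population with no condition on SNaP receipt: eligibility (3.2.1, 3.3, 3.4), the consent process (5.5), the Table 2 data source (records of consenting PWID), the Aim 3 site target of 70% uptake (5.4, 7.5) and the sample of 6200 (3.5.1, 8.1.2).

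**The concern.** Two analysts, one following the opening sentence of Section 7.3.1 and one following the definition, could compute different primary results from the same data. The definition is the sentence that would normally be programmed.

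The choice matters because sites are the randomized unit, so an individual's receipt of SNaP comes after randomization. It also comes after enrollment: recruitment directly follows post-test counseling (3.5.1), while the counseling and navigation sessions fall within 4 and 8 weeks of enrollment (4.1). The conceptual framework in Section 1.3 expects tailoring to improve implementation and places high penetration on the route to ART uptake. Restricting the comparison to recipients therefore conditions on a step between the randomized strategy and the outcome. Any gain that TA makes by reaching more PWID drops out, and the sign can reverse if the additional PWID reached start ART less often.

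The ambiguity carries into Aim 2, because the primary cost-effectiveness ratio in Section 2.1 is cost per incremental ART uptake.

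**Working it through.** **The plan's own figures.** Section 3.5.1: 335 × 21 = 7035; less 12% deaths, 7035 × 0.88 = 6191, or about 6200. Nothing is deducted for people who decline SNaP. Mean cluster size is 6200/42 = 147.6. The design effect is 1 + (147.6 − 1) × ICC, which gives 2.47 at ICC 0.01 and 8.33 at ICC 0.05. With 3100 per arm, two-sided α = 0.05, unpooled variance and equal cluster sizes:
- 70% vs 60%, ICC 0.05: SE = √[(0.21 + 0.24) × 8.33/3100] = 0.0348; z = 0.10/0.0348 − 1.96 = 0.92; power 82.0%.
- 70% vs 64%, ICC 0.01: SE = √[(0.21 + 0.2304) × 2.47/3100] = 0.0187; z = 0.06/0.0187 − 1.96 = 1.25; power 89.4%.

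The stated power above 80% is reproduced, and it rests on all 6200, not on recipients.

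**Effect of the denominator.** The documents give no reach figures, so every rate below is an assumption. Let r be reach in each arm, p1 uptake in SA recipients, p0 uptake in non-recipients of both arms, and pa uptake in the additional PWID reached under TA. The TA minus SA differences are:
- All eligible: (rTA − rSA) × (pa − p0)
- Recipients only: (rTA − rSA) × (pa − p1) / rTA

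With p1 = 70% and p0 = 30%:

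| Reach, SA vs TA | pa | All eligible | Recipients only |
|---|---|---|---|
| 65% vs 70% | 70% | 0.05 × 0.40 = +2 points | 0 |
| 65% vs 70% | 50% | 0.05 × 0.20 = +1 | 0.05 × (−0.20)/0.70 = −1.4 |
| 75% vs 80% | 70% | +2 | 0 |
| 75% vs 80% | 50% | +1 | 0.05 × (−0.20)/0.80 = −1.25 |
| 65% vs 80% | 70% | 0.15 × 0.40 = +6 | 0 |
| 65% vs 80% | 50% | 0.15 × 0.20 = +3 | 0.15 × (−0.20)/0.80 = −3.75 |
| Equal reach, same mix | – | 0 | 0 |

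**Range.** When pa = p1, the hidden difference is (rTA − rSA) × (p1 − p0). For a 5-point reach gap and an uptake contrast of 20, 40 or 60 points it is 1, 2 or 3 points. To hide the full 6 points that Section 8.1.2 is powered for at ICC 0.01, the reach gap would have to be 6/0.20 = 30, 6/0.40 = 15 or 6/0.60 = 10 points.

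**A null case.** Suppose TA changes nobody's ART uptake. In both arms 80% of PWID would receive SNaP (uptake 75%), and TA adds another 10% (uptake 50%, the same as they would have without it). The remaining 10% have 40%. Among all eligible PWID both arms have 0.80 × 0.75 + 0.10 × 0.50 + 0.10 × 0.40 = 69%, a difference of 0. Among recipients TA has (0.80 × 0.75 + 0.10 × 0.50)/0.90 = 72.2% against 75% in SA, a spurious −2.8 points.

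**The case against.** The strongest reply is that this is one loose phrase. Section 4.1 says PWID confirmed positive at a site will get SNaP, Section 5.5 treats it as routine clinical activity there, and Section 5.5.1.1 offers it to all PWID who present. On that view, receiving SNaP just means being a client of a SNaP site. Table 2, the Aim 3 target and the intent-to-treat statement agree with this, and no section plans a recipients-only analysis. Bias would also need three things together: the literal reading is used, reach differs by arm, and recipients differ from non-recipients in uptake.

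Much of this stands. The intended population can be inferred, and the harm is conditional and unquantified. But no section says that receiving SNaP means being eligible or enrolled, and the plan itself distinguishes recipients from decliners.

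Three narrower points have some force:
- The interviews with decliners are weak evidence against the enrollment condition in Section 5.5.1. They appear in the schedule for enrolled PWID, but they carry their own consent, so decliners could be interviewed without having been enrolled.
- The 6200 excludes expected deaths, and Section 7.3.1 does not say how deaths are counted. That is a separate question, which correcting this denominator does not settle.
- Consent also follows site randomization, so even the consenting population is selected. Reporting consent by arm describes that selection but does not remove it.

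**Conclusion.** The concern holds. Consecutive sentences of Section 7.3.1 give the primary effectiveness outcome two denominators, and the defining one, taken literally, is not an intent-to-treat comparison. That the two wordings conflict is certain; how much it would matter is not. On the assumed rates, a 5-point reach gap hides 1 to 3 points of true difference, and the sign reverses if the added recipients have lower uptake. Removing the whole 6-point difference would take a reach gap of 10 to 30 points. Equal reach with the same mix of recipients gives no bias. It should be fixed: the intended population can be inferred, but the denominator of a primary outcome should not be left to the analyst.

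**What to change.** - **Section 7.3.1:** make the denominator in the defining sentence *all eligible consenting PWID at each randomized site, whether or not SNaP was accepted or delivered*. Leave the numerator and its acceptable evidence as they are.
- **Table 2:** state the same denominator.
- **Section 5.5.1:** delete acceptance of SNaP as a condition for the enrollment steps, so that it agrees with the consent process in Section 5.5.
- **Reporting:** present uptake among SNaP recipients as descriptive only. Report consent and decline counts by arm (Section 8.3 already tracks refusals), with the routine testing log in Section 5.5 as context for all diagnosed PWID.

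The cost is wording, plus record look-ups for consenting decliners within the existing semi-annual extraction: 6200 × 0.10 = 620 records per 10 points of non-receipt, or 7035 × 0.10 ≈ 700 on the number recruited. This assumes decliners were offered the record-access consent, as Section 5.5 provides for every confirmed HIV-infected PWID. If a site instead applied the acceptance condition in Section 5.5.1, decliners who never consented cannot be added by look-up, and their number should be reported. The sample size does not change.

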### **7.3.2 Secondary Effectiveness Outcomes**

The secondary effectiveness outcomes include the following two measures (**Table 2**):

- Viral suppression, defined as an undetectable viral load on a dried-blood spot sample.
- MAT uptake, evidence of MAT use from MAT clinic records, defined as MAT initiation among those not currently on MAT

**Table 2. Study Outcomes**

Outcome	Definition	Measure or Scale*
Primary Integration Implementation Outcome		
Fidelity to SNaP protocol	Delivering SNaP as intended.	(systems navigation % * average quality score) + (counseling session % * average quality score) [see text for example]
Secondary SNaP Implementation Outcomes		
Penetration	% of PWID contacted, & enrolled in SNaP	Proportion of newly diagnosed or previously diagnosed and not currently on ART PWID at test sites who are contacted by a navigator and/or counselor and participate in a SNaP session.
Acceptability	Perception that SNaP is agreeable, palatable, or satisfactory.	OADRI (adapted): 12-item scale, staff and client acceptability of an innovation in a clinic setting.  and qualitative interviews
Implementation costs	Costs of SNaP & its implementation	Directly measured non-research costs (Aim 2)
Primary Effectiveness Outcome		
Uptake of ART	% PWID who initiated ART	ART clinic records of consenting PWID
Secondary Effectiveness Outcomes		
Viral suppression	% PWID virally suppressed	Undetectable viral load on DBS**, in PWID subsample cohort
Uptake of MAT	% of PWID on MAT	MAT clinic records of consenting PWID

\*All measures will be adapted to SNaP; \*\*DBS=dried blood spot

#### 7.4. Cost-Effectiveness Measurements (Aim 2)

We will conduct an empirical costing study of SNaP—including SA and TA and the actual process of implementation itself—from a societal perspective. We will estimate implementation costs prospectively by embedding a trained costing specialist within each Intervention Mapping team, documenting all resources used (e.g., staff training level and time, travel costs, supplies, etc.) and estimating the unit cost of each resource. To estimate the unit health system cost of each intervention, we will perform detailed budgetary analysis including interviews of key staff, review of logbooks/timesheets, and time-and-motion studies to record navigator, counselor, and other staff time devoted to various activities on ≥15 randomly selected days, conducted by the costing specialists, in each of 12 clinic sites (6 sites per arm, selected purposively to provide representation of patient volume, urban/rural status, and geography) over the course of the trial. To estimate patient costs, we will administer a survey to a smaller subset of the 1500 PWID subsample cohort at baseline, and a single follow-up visit of 12 or 18 or 24 months, depending on PWID enrollment time to collect data on direct and indirect (lost wages, child care, etc.) costs of clinic visits and other elements (e.g., medication side effects) associated with ART, MAT, and SNaP itself. Cost data collection will be based on the Tool to Estimate Patient Costs, which we have adapted and used in Uganda.

We will use, in our primary analysis, an “ingredients” or bottom-up approach, with comparison to “top-down” costing. Our comprehensive costing will include costs associated with each component of each delivery strategy (e.g., staff, equipment, consumables, overheads, etc.), and will follow international conventions for all procedures including economic costing, discounting, and reporting.

#### 7.5. High and Low Performing Sites (Aim 3)

Our *a priori* definition of successful implementation at 24 months is a site with a fidelity score of

136 (see Section 7.2) and 70% ART uptake among its newly diagnosed or previously diagnosed and not currently on ART PWID clients.

## 8. STATISTICAL CONSIDERATIONS

### 8.1. Power and Sample Size Considerations

#### 8.1.1 *Implementation Outcomes Sample Size Calculations*

The **primary implementation outcome is fidelity**, based on an index with a score ranging from 0-200 (see Section 7.2). The **unit of analysis is test site** (n=42 test sites total, 21 per arm).

In HPTN 074, the Vietnam site achieved 86%-88% completion of navigation and counseling sessions in the protocol-specified window, and in our counseling studies we consistently achieve 90-95% quality scores on supervisor-rated counseling sessions. **This track record suggests a “best case” upper bound to the fidelity score of ~150** [(100\*0.85 navigation sessions completed \* 0.9 quality) + (100\*0.85 counseling sessions completed \* 0.9 quality) = 76.5+76.5 = 153].

**We expect TA to achieve close to this “best case” upper bound, with  $\geq 80\%$  appointment completion and  $\geq 85\%$  quality scores, or a fidelity score of  $\geq 136$  = (100\*0.8\*0.85 + 100\*0.8\*0.85). We expect IM to achieve lower session completion and lower quality.**

*Using two-tailed tests and  $\alpha=0.05$  and assuming a conservatively large standard deviation of 40, 42 sites will give us 80% power to detect a difference between a fidelity score of 136 in the TA arm and 100.5 in the SA arm.*

A score of 100.5 in the TA arm corresponds to 75% session completion and 67% average quality ratings (100\*0.75\*0.67 + 100\*0.75\*0.67 =100.5).

With a more plausible standard deviation of 28, we would have 80% power to detect the difference between a score of 136 in the TA arm and 111 (75% completion,74% quality) in the SA arm. Thus, we have power to detect operationally meaningful differences in session completion and quality scores.

#### 8.1.2 *Effectiveness Outcomes Sample Size Calculations*

The **primary effectiveness outcome is ART uptake**, measured as a dichotomous variable at the PWID level. After accounting for up to 12% mortality during follow-up, we estimate an available sample of 6200 PWID, with cluster (test site) size ranging from 7-764 PWID (mean≈148). **Loss to follow-up does not affect this outcome**, as patients not retained in clinic will be assumed not to be on ART.

**To calculate the design effect**, we estimate that the intra-cluster correlation coefficient may range from 0.01-0.05, as is typical in clinic-level behavioral interventions, implying a design effect between 2.5 and 8.4.

Using two-tailed tests and  $\alpha=0.05$ , we will have >80% power to detect a difference as small as 10 percentage points (e.g., 70% vs. 60% ART uptake) if the ICC is as large as 0.05, and as small as 6 percentage points (e.g., 70% vs. 64% ART uptake) if the ICC is as small as 0.01. Thus, we are well powered to detect operationally meaningful differences in our primary effectiveness outcome of ART uptake.

For **viral load**, which is based on a sample of  $n=1200$  (~30 per clinic), assuming the same ICC of 0.01-0.05, we will have 80% power to detect differences of 10-14 percentage points in viral suppression between arms (e.g. 40% vs. 30% if  $ICC=0.01$ ; 40% vs. 26% if  $ICC=0.05$ ).

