#### **5.1.4 Randomization**

We obtained a complete list of the 136 HIV test sites in Vietnam, including the number of persons tested per month, positivity rates, and proportion of PWID. These data have been used to identify 42 proposed test sites for inclusion in this implementation study.

Test sites will be stratified by region and size, then randomized to either arm at a 1:1 ratio (21 sites per trial arm). Randomization will be blocked within strata to ensure equal distribution by arm.

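### The ART uptake power in Section 8.1.2 assumes equal-sized sites; with the stated 7 to 764 range and patients weighted equally, power for 10 points at ICC 0.05 is about 68-72%, not above 80%

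*Combined protocol and SAP*

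**What the plan says.** Section 8.1.2 sizes ART uptake on 6200 patients at 42 sites, "with cluster (test site) size ranging from 7-764 PWID" and a mean of about 148. It takes an ICC between 0.01 and 0.05, "implying a design effect between 2.5 and 8.4". With two-sided tests at alpha 0.05 it concludes that "we will have >80% power to detect a difference as small as 10 percentage points (e.g., 70% vs. 60% ART uptake") at ICC 0.05, and a difference "as small as 6 percentage points (e.g., 70% vs. 64% ART uptake) if the ICC is as small as 0.01".

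Section 8.2.1 analyses ART uptake with a patient-level generalized linear model (identity link, binomial errors). On clustering it says only that "the design effect introduced by clinic-level randomization will be addressed using a robust variance estimate". It gives no working correlation, cluster weights, random effect or stratum terms.

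Section 5.1.4 says the investigators hold a list of all test sites, "including the number of persons tested per month, positivity rates, and proportion of PWID". It also says: "Test sites will be stratified by region and size, then randomized to either arm at a 1:1 ratio".

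**The concern.** The two design effects come from the formula for clusters of one common size, yet the paragraph that reports them describes a roughly hundredfold spread in site size. When patients are weighted equally, a site of 764 dominates its arm's estimate and brings its own site effect with it. The variance then exceeds what the mean size alone suggests. A robust variance will report that larger variance honestly, but it does not recover the lost precision.

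What is at stake is the planning claim for a primary outcome. Someone reading a null result against a stated power above 80% would be too confident that a 10-point difference had been ruled out. The estimate and its robust confidence interval are not in question.

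**Working it through.** **Inputs.** From Section 8.1.2: N = 6200, site sizes 7 to 764, ICC 0.01 to 0.05, 70% vs 60% (or 64%), two-sided alpha 0.05. From Section 2.2: 42 sites allocated 1:1, so 21 per arm. The mean size is 6200/42 = 147.6. Power is by normal approximation, Φ(difference/SE − 1.96), unless marked t (40 df).

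**1. The plan's own figures.** The equal-cluster design effect is DE = 1 + (m − 1) × ICC.
- With m = 148: 1 + 147 × 0.01 = 2.47 and 1 + 147 × 0.05 = 8.35. These are the stated 2.5 and 8.4.
- At ICC 0.05, 3100/8.35 = 371 effective patients per arm. SE = √((0.21 + 0.24)/371) = 0.0348 and power is 82% (80% with t). The claim reproduces for equal sites, with little slack.

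**2. Smallest possible CV.** With one site of 7, one of 764 and the total fixed, the spread is least when the other 40 sites are equal: (6200 − 771)/40 = 135.7 each.
- Sum of squares: 7² + 764² + 40 × 135.725² = 1,320,596.
- Variance: 1,320,596/42 − 147.62² ≈ 9,651. SD 98.2; CV = 98.2/147.6 = 0.67.

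Any other spread of the 40 sites gives a larger CV.

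**3. Equal patient weights, standard formula.** DE = 1 + ((1 + CV²) × m − 1) × ICC.
- DE = 1 + (1.443 × 147.6 − 1) × 0.05 = 11.6.
- 3100/11.6 = 267 per arm; SE = √(0.45/267) = 0.0410.
- Power = Φ(0.10/0.0410 − 1.96) = 68% (66% with t). The difference detectable with 80% power is 11.5 points.

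**4. Equal patient weights, site by site.** Within an arm the variance is p(1 − p)[(1 − ICC)/N + ICC × Σn²/N²]. Put the 764 site in the tailored arm (N = 3478.5, Σn² = 952,122) and the 7 site in the standard arm (N = 2721.5, Σn² = 368,475):
- Tailored: 0.21 × (0.000273 + 0.003934) = 0.000884.
- Standard: 0.24 × (0.000349 + 0.002488) = 0.000681.
- SE = √0.001564 = 0.0396; power 71.5%.

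Over all four placements of the two extreme sites, SE is 0.0396 to 0.0405 and power 70% to 72% (67% to 69% with t). The detectable difference is 11.1 to 11.4 points. A search over arm totals finds a maximum of 75%, reached only with a split of about 4,666 vs 1,534 patients, which is unrealistic under size-stratified 1:1 allocation.

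**5. Efficient weights, same layout.** Each site contributes n/(1 + (n − 1) × 0.05): 19.5 for the 764 site, 5.4 for the 7 site and 17.54 for each of the other 40. The total is 726.7, or 363 per arm. SE = 0.0352 and power 81% (79% with t).

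**6. Sensitivity.** The true CV is not in the documents; 0.8 and 1.0 below are assumptions.

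| Power | CV 0 | CV 0.67 (minimum) | CV 0.8 | CV 1.0 |
|---|---|---|---|---|
| 10 points, ICC 0.05, equal weights (formula) | 82% | 68% | 63% | 55% |
| 10 points, ICC 0.05, efficient weights | 82% | 81% | 80% | 78% |
| 6 points, ICC 0.01, equal weights (formula) | 89% | 81% | 78% | 72% |

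The efficient-weight entries at CV 0.8 and 1.0 also assume lognormal site sizes with one site fixed at 7 and one at 764. At the minimum CV with equal weights, 10 points keeps 80% power up to an ICC of about 0.037 (formula) or 0.038 to 0.040 (site by site).

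**The case against.** The strongest reply is that the shortfall rests on silence. A robust variance is also used with an exchangeable working correlation, and under those weights power at the minimum CV is 81%, so the claim just holds. This stands as a reason to specify the weighting. It does not rescue the text: a binomial model with a robust variance and nothing more weights patients equally, and even the efficient figure has almost no margin. The 79% under efficient weights owes more to the t reference than to unequal sizes, since the same reference takes equal clusters from 82% to 80%.

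The shortfall is also confined to the upper part of the ICC range, and it depends on the example proportions. With 80% vs 70%, the site-by-site calculation gives about 77% to 80% power at ICC 0.05. Both points are fair, but the protocol chose the 0.05 bound and the 70% vs 60% example and attached its power figure to them.

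Stratification by region and size could reduce between-site variance if the analysis adjusted for the strata. Section 8.2.1 names no such terms and the documents give no figure for the gain, so none is credited here.

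Finally, nothing is miscalculated within the formula used. The fault is that the formula leaves out a feature stated in the same paragraph.

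**Conclusion.** The concern holds. Under the analysis as written, with patients weighted equally, power for 70% vs 60% at ICC 0.05 is about 68% to 72% at the smallest CV the protocol's own range allows. At that CV the chance of missing a true 10-point difference is about 28% to 32%, rather than under 20%. A more uneven spread among the other 40 sites would generally lower power further, and no layout with one site of 7 and one of 764 exceeds 75%.

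The result assumes 6200 patients, 21 sites per arm, no stratum adjustment and the normal approximation. If exchangeable weights are intended, the claim is marginal rather than wrong, but the plan needs to say so. The defect should be corrected. It concerns the power statement only.

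**What to change.** 1. Compute the CV of expected site sizes from the counts described in Section 5.1.4.
2. In Section 8.2.1, state the working correlation or weighting, clustered on test site, and whether the region and size strata enter the model.
3. Restate Section 8.1.2, for example: *Expected site sizes have CV [value]. With [independence / exchangeable] working correlation clustered on test site, the design effect is [1 + ((1 + CV²) × mean − 1) × ICC for independence; from site-by-site variances for exchangeable]. Power for 70% vs 60% at ICC 0.05 is [value]; the difference detectable with 80% power is [value] at ICC 0.05 and [value] at ICC 0.01.*
4. Drop the claim of more than 80% power for 10 points at ICC 0.05 unless the recomputation supports it.

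The cost is one paragraph in 8.1.2 and a sentence in 8.2.1, with no added enrolment, though the stated power will probably look less favourable. Exchangeable weights recover most of the loss but give patients at large sites less weight in the estimate. The choice should therefore be fixed before the arms are compared.
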